### 5.5.3 AE, Exposure and Other

- AEs, drug-related AEs, and SAEs will be summarized in number (%) of patients.
- AEs of interest (Bone fractures, Diabetes mellitus and hyperglycemia, Fall, Fatigue/ asthenic conditions, Weight loss, Interstitial lung disease, Rash, Seizure, Hypertension, Mental impairment disorders, Depressed mood disorders, Breast disorders/gynecomastia, Cardiac disorders, Coronary artery disorders, Cerebral ischaemia, Cerebral and intracranial hemorrhage) will be summarized descriptively.
- Time to deterioration of KPS will be calculated as the time from randomization (or time from first dose in the lead-in phase) to the first date the patient had a decline in KPS of at least 10 points. In the event of no deterioration of KPS, the time to deterioration of KPS will be censored at the last evaluable assessment. Time to deterioration of KPS will be analyzed and presented the same way as the time to PSA progression.
- Treatment exposure of the study intervention, including time on treatment and dose changes, will be summarized.

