
Objectives	Endpoints
	
Depression:
 
 • Proportion of participants with a worsening in scores in the PHQ-9 during the 24 weeks and 52 weeks from baseline. Worsening is defined as an increase of at least 1 point in worst level of depression from baseline by 24 weeks and 52 weeks. 
Safety
 
 • All treatment emergent AEs, SAEs, and AEs leading to discontinuation • AEs of interest, including falls, fractures, and hypothyroidism 
Exposure and other:
 
 • Time to deterioration of KPS defined as at least a 10 point decline from baseline • Treatment exposure of the study intervention including time on treatment • Dose reductions of study intervention • Time to PSA progression (as per PCWG3 criteria) • Survival status

4. Study Design

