	
  
 Test	Reliable Change Index threshold (from baseline)	
   
 Hopkins Verbal Learning Test - Revised Total Recall (HVLTR TR)	±5 words	
 
 Hopkins Verbal Learning Test - Revised Delayed Recall (HVLTR DR)	±3 words	
 
 Hopkins Verbal Learning Test - Revised Delayed Recognition (HVLTR RECOG)	±2 words	
 
 Trail Making Test: Part A (TMTA)	±12 seconds	
 
 Trail Making Test: Part B (TMTB)	±26 seconds	
 
 Controlled Oral Word Association (COWA)	±12 words	
  
 
 • The proportion of participants with a decline of >10 points from baseline in the FACT-Cog domain by 24 and 52 weeks will be summarized. 
Fatigue
 
 • The proportion of participants with an increase of at least 1 point in worst level of fatigue from baseline during the past 24 hours (item 3 of BFI) by 24 and 52 weeks will be summarized. • Similarly, the proportion of participants with an increase of at least 1 point in in fatigue interference from baseline during the past 24 hours (items 4A through F of BFI) by 24 and 52 weeks will be summarized. The proportion of participants with a decline and the 95% CIs will be summarized for each treatment arm. This rate will be compared between the two arms using Cochran-Mantel-Haenszel test adjusting for stratification factors as captured by IWRS. 
Depression
 
 • The proportion of participants with a worsening of scores by PHQ-9 during the 24 and 52 week period from baseline will be summarized. Worsening is defined as an increase of at least 1 point in worst level of depression from baseline by 24 weeks and 52 weeks. 
AE, Exposure, other
 
 • AEs, drug-related AEs, and SAEs will be summarized by MedDRA coding system and NCI-CTCAE version 5.0 worst grade. • AE of interest (fall, fracture, hypothyroidism) will be summarized descriptively. • Time to deterioration of KPS will be calculated as the time from randomization (or time from first dose for participants in the lead-in phase) to the first date the participant had a decline in KPS score of at least 10 points. Data will be summarized using the Kaplan-Meier method. • Treatment exposure of the study intervention, including time on treatment and dose reductions, will be summarized. 		Test	Reliable Change Index threshold (from baseline)	Hopkins Verbal Learning Test - Revised Total Recall (HVLTR TR)	±5 words	Hopkins Verbal Learning Test - Revised Delayed Recall (HVLTR DR)	±3 words	Hopkins Verbal Learning Test - Revised Delayed Recognition (HVLTR RECOG)	±2 words	Trail Making Test: Part A (TMTA)	±12 seconds	Trail Making Test: Part B (TMTB)	±26 seconds	Controlled Oral Word Association (COWA)	±12 words

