
(HVLt-R), Trail Making Test (TMT), Controlled Oral Word Association (COWA), and Functional Assessment of Cancer Therapy – Cognitive questionnaire (FACT-Cog).
 
 
Compare the effects of treatment with darolutamide vs. enzalutamide on fatigue as assessed by the Brief Fatigue Inventory (BFI).
 
Compare the effects of treatment with darolutamide vs. enzalutamide on depression as assessed by the Patient Health Questionnaire-9 (PHQ-9).
 
Evaluate safety, including AEs of special interest (AESI), of participants treated with darolutamide vs. enzalutamide.
 
Evaluate the effect of treatment with darolutamide or enzalutamide on prostate-specific antigen (PSA), survival status, and exposure.
 
	
 
Proportion of participants with a decline using a selected domain of FACT-Cog. Decline is defined as a decrease of >10 points during the 24 weeks and 52 weeks from baseline.
 
 
Fatigue:
 
 
Proportion of participants with a worsening of fatigue during the 24 weeks and 52 weeks from baseline. Worsening is defined as an increase of at least 1 point in worst level of fatigue from baseline by 24 weeks and 52 weeks (based on item 3 of the BFI).
 
Proportion of participants with an increase of at least 1 point in fatigue interference by 24 weeks and 52 weeks from baseline (based on items 4A-F of the BFI).
 
 
Depression:
 
 
Proportion of participants with a worsening in scores in the PHQ-9 during the 24 weeks and 52 weeks from baseline. Worsening is defined as an increase of at least 1 point in worst level of depression from baseline by 24 weeks and 52 weeks.
 
 
Safety
 
 
All treatment emergent AEs (TEAEs), serious adverse events (SAEs), and AEs leading to study intervention discontinuation.
 
AEs of interest listed in section 5.5.3.
 
 
Exposure and other:
 
 
Treatment exposure of the study intervention (defined as investigational intervention, protocol; Darolutamide or Enzalutamide) including time on treatment.
 
Dose reductions of study intervention.
 
Time to PSA progression (as per Prostate Cancer Working Group [PCWG3] criteria).
 
Survival status.
 

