#### 5.5.5 Adverse Events

A TEAE is defined as any event arising or worsening after first dose study drug until 30 days after last dose. If an AE occurs before the first dose of treatment it will be considered a non-treatment emergent AE.

TEAEs and AEs will be summarized by frequency and percentage of patients and tabulated by MedDRA system organ class (SOC) and preferred term (PT), by maximum NCI-CTCAE version 5.0 grade and by drug relationship as not related and related to treatment. SAEs, TEAEs leading to treatment discontinuation and deaths will be summarized. Drug-related TEAEs by CTCAE grade, and drug-related grade 3 or higher TEAEs are summarized. Patients with multiple TEAEs or AEs are counted once within a summary category-SOC, PT, maximum grade, or relationship to treatments.

AESI be summarized by SOC and PT and grade in separate summary tables. All AEs will be listed.

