## **6.0 Changes to Planned Analyses**

Not applicable.

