AE = adverse event; BFI = Brief Fatigue Inventory; COWA = Controlled Oral Word Association; CRF = case report form; HVLt-R = Hopkins Verbal

Learning Test - Revised; PHQ-9 = Patient health questionnaire-9; PSA = prostate-specific antigen; SPPB = Short Physical Performance Battery; TMT = Trail Making Test; TUG = Timed Up and Go

- a PSA will be assessed at the same time as other laboratory assessments. A time window of  $\pm$  14 days is allowed for laboratory and PSA assessments.
- b Including survival, pain, radiographic progression, metastases, and skeletal events
- c AEs of interest are fractures, falls, and hypothyroidism
- d Physical function tests include SPPB and the TUG assessment.
- e Accelerometry assessment will require the participant to wear an accelerometry device on the wrist or hip for a minimum of 7 days at each time point. The first accelerometry assessment is to be performed before the first dose (i.e. during screening).
- f Cognitive function tests include the HVLT-R, TMT, and COWA, as well as the patient-reported outcome questionnaire FACT-Cog.
- g BFI is a 5 minute self-assessment tool that identifies fatigue in cancer participants over a 24-hour period.
- h The first TUG assessment is to be performed before the first dose (either during screening or Week 1 Day 1).
- i Once the baseline procedures are completed, the first administration of study intervention will be provided at the study center and the participant will be provided with additional medication to take as scheduled through the Week 4 visit. (Each participant will be instructed to bring any remaining drug back to the center at the Week 4 visit.)
- j At this and each subsequent visit, the participant will return dispensed but unused study intervention to the investigator for recording on the CRF. Reasons for non-compliance will be recorded. A new supply of study drug sufficient to meet the dosing requirements of each participant will be dispensed.
- k Participants remaining on treatment beyond Week 52 will continue, where possible, to receive study intervention and assessments until the final evaluation of the randomized phase (i.e. at Week 52 for the last participant, see Protocol Section 4.4.1)
- l Prior to the final evaluation of the randomized phase of the study, all participants will go into Week 53 active follow-up or survival follow-up as applicable.

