## 9.0 Index of Outputs for Lead-in Phase

Table 1	Study Population
Table 2	Patient Disposition
Table 3	Demographics and Subject Characteristics
Table 4	Prostate Cancer Classification
Table 5.1	Systemic Anti-Cancer Therapy
Table 5.2	Prior Radiotherapy and Prior Surgery
Table 7	Summary of Treatment-Emergent Adverse Events by System Organ Class
Table 8	Drug-Related Treatment-Emergent Adverse Events by System Organ Class and Preferred Term
Table 9	Grade 3 or Greater, Drug-Related, Treatment-Emergent Adverse Events by System Organ Class and Preferred Term
Table 10	Summary of Serious Adverse Events by System Organ Class and Preferred Term
Table 17.1	Proportion of Patients with a Worsening in TUG time
Table 17.2	Timed Up and Go (TUG) by CRPC Metastatic Status
Table 17.3	Short Physical Performance Battery: Change from Baseline in Total Score and Proportion of Patients with Worsening in Total Score
Table 17.4	Short Physical Performance Battery by CRPC Metastatic Status: Change from Baseline in Total Score and Proportion of Patients with Worsening in Total Score
Table 17.5	Cognitive Function Tests: Proportion of Patients who have Decline / No Change / Improvement for Reliable Change Index (RCI) from Baseline
Table 17.6	Proportion of Participants with a Decline of >10 points from Baseline in FACT-Cog
Table 18.1	Proportion of Patients with a Decline in Fatigue Interference from Baseline

Table 23.1	Average Counts Per Minute from Accelerometry (CPM) – Descriptive Statistics
Table 23.2	Average Counts Per Minute from Accelerometry (CPM) by CRPC metastatic status
Table 23.3	Average Counts Per Minute (log-transformed) from Accelerometry (CPM) by CRPC metastatic status
Table 23.7	
Table 24.1	Proportion of Time Spent in Each Daily Activity Category: Light, Moderate and Vigorous Mean Change from Baseline in Proportion of Time Spent in Each Daily Activity Category: Light, Moderate and Vigorous
Table 25.1	PSA response by CRPC metastatic status
Table 25.2	Kaplan-Meier Analysis of Time to PSA Progression Based on PCWG3
Listing 16.2.1.1	Inclusion/Exclusion Criteria
Listing 16.2.1.2	Patient Disposition
Listing 16.2.4.1	Demographics and Subject Characteristics
Listing 16.2.4.3	Medical History
Listing 16.2.4.8	Prior Medications
Listing 16.2.4.9	Concomitant Medications
Listing 16.2.6.1	Timed Up and Go
Listing 16.2.6.2	Short Physical Performance Battery
Listing 16.2.6.3	Cognitive Function Tests
Listing 16.2.6.4	Accelerometry: Average CPM
Listing 16.2.6.5	Fatigue Interference

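### SAP 5.5.3 leaves hypothyroidism out of its list of adverse events of interest, so a summary planned in Protocol 9.4.2 would not be produced

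*SAP*

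**What the plan says.** The protocol names the same three events throughout. The secondary safety endpoint in Section 3 reads "AEs of interest, including falls, fractures, and hypothyroidism", and the planned analysis in Section 9.4.2 reads "AE of interest (fall, fracture, hypothyroidism) will be summarized descriptively". Section 8.2 adds that these events are to be captured by dedicated CRF questions.

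The SAP defines the endpoint differently. Its Table 1 gives the safety endpoint as "AEs of interest listed in section 5.5.3". That section opens its list with "AEs of interest (Bone fractures, Diabetes mellitus and hyperglycemia, Fall, Fatigue/ asthenic conditions, Weight loss, Interstitial lung disease, Rash, Seizure, Hypertension" and continues with seven further categories, none of them thyroid-related. Section 5.5.5 then plans the output: "AESI be summarized by SOC and PT and grade in separate summary tables".

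Elsewhere the SAP keeps the protocol's definition. Footnote c under its schedules of activities, Table 8-1 for the lead-in phase and Table 8-2 for the randomized phase, states "AEs of interest are fractures, falls, and hypothyroidism". SAP 6.0, where departures from the protocol's analyses would be recorded, says only "Not applicable".

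**The concern.** A SAP may widen or narrow a list of events of interest, but it should say that it has done so. Here the list was widened well beyond the protocol's three events, and one of those three disappeared. Nothing shows whether this was a decision or a slip. Protocol 2.2 discusses rash and hypothyroidism together when it contrasts the AR inhibitors. The SAP list has rash but not hypothyroidism, which fits an oversight but does not prove one.

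At stake is a protocol-named part of a secondary safety endpoint, in a study whose rationale is a differentiated safety profile. The protocol also gives events of interest special handling: dedicated CRF questions (8.2), follow-up regardless of causality (8.3), and follow-up of non-serious cases until resolution or stabilization (8.3.3). Collecting an event this way and then planning no dedicated display leaves a gap between collection and analysis. The SAP also holds two definitions of the same term, so its reader cannot tell which was meant.

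**Working it through.** No calculation applies. The check is a comparison of lists and a tracing of which list governs the output.

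**Step 1: the protocol's set.** Falls, fractures, hypothyroidism: 3 events.

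**Step 2: the SAP 5.5.3 set, regrouped by body system.**

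| Group | Items in SAP 5.5.3 | Count |
|---|---|---|
| Falls and bone | fall; bone fractures | 2 |
| Metabolic | diabetes mellitus with hyperglycemia; weight loss | 2 |
| General | fatigue or asthenic conditions | 1 |
| Lung | interstitial lung disease | 1 |
| Skin | rash | 1 |
| Neuropsychiatric | seizure; depressed mood; mental impairment | 3 |
| Cardiovascular | hypertension; coronary artery; cardiac | 3 |
| Cerebrovascular | hemorrhage (cerebral and intracranial); ischaemia | 2 |
| Breast | breast disorders or gynecomastia | 1 |
| Thyroid or general endocrine | none | 0 |

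Total: 2 + 2 + 1 + 1 + 1 + 3 + 3 + 2 + 1 + 0 = 16. No wording marks the items as examples, so the list is closed.

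**Step 3: compare.**

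- In both sets: fall and fracture, 2 of the protocol's 3.
- In the protocol only: hypothyroidism, 1 of 3.
- In the SAP only: 16 − 2 = 14 items.

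**Step 4: how often hypothyroidism is named as an event of interest.**

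- Protocol: synopsis endpoints; footnote c of Table 1-1; footnote c of Table 1-2; Section 3; Section 8.2; Section 9.4.2. That is 6.
- SAP: footnote c of Table 8-1; footnote c of Table 8-2. That is 2.
- Total: 6 + 2 = 8. Several of these repeat one another, so the count shows consistency, not weight.

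**Step 5: which list governs.** SAP Table 1 defines the endpoint by reference to 5.5.3, and the analysis text gives no other definition for the separate tables in 5.5.5. A programmer working from the SAP would therefore include no hypothyroidism entry in either output.

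**Step 6: what would still be reported.** SAP 5.5.5 tabulates all treatment-emergent events by system organ class, preferred term, maximum grade and relationship, and lists every event. Reported hypothyroidism would appear there, counted by preferred term. Those tables give no single patient count across related thyroid terms. The laboratory summaries do not clearly fill the gap: SAP 5.5.6 summarizes hematology, chemistry and urinalysis, while Protocol Table 10-1 places TSH under other screening tests.

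**Step 7: the lead-in outputs.** SAP 9.0 names four adverse event tables, 7 to 10, the last being "Summary of Serious Adverse Events by System Organ Class and Preferred Term". None is a table of events of interest, for any event, so the index does not supply the missing summary.

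**The case against.** The strongest reply is that little is lost. Protocol 9.4.2 asks only for a descriptive summary, not a separate table. The general tables of treatment-emergent events would give counts of reported hypothyroidism, shown by arm in the randomized phase. This is right about the data: the counts survive. It does not meet the point that the protocol names this event for an event-of-interest summary and the SAP gives that summary to the other two events only.

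A second reply is that footnote c was carried over from the protocol's schedules and annotates a site review row, so SAP 5.5.3 is the one operative list for analysis. That is a fair reading of how the mismatch arose. It also confirms that the operative list is the one without hypothyroidism, and the footnotes would still need reconciling.

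Third, neither document specifies a MedDRA grouping for hypothyroidism, and SAP 5.5.3 defines none for its other items. So a grouping is not a documented output that has been lost. It remains a reasonable request, because the SAP list is made up largely of grouped categories that need term definitions to be programmed.

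Fourth, adding a term to 5.5.3 changes no named lead-in output, and the randomized phase is conditional on the lead-in findings. That stands, and it limits the practical effect. The numbering in the SAP 9.0 index jumps from Table 10 to Table 17.1, so the index may be incomplete and cannot show that no such table was planned.

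**Conclusion.** The concern holds. One of the three adverse events of interest named in the protocol is absent from the closed 16-item list that defines the endpoint in the SAP. The omission contradicts Protocol 9.4.2 and the SAP's own schedule footnotes, and SAP 6.0 does not declare it. Applied as written, the plan yields no event-of-interest summary for hypothyroidism and no entry in the separate tables of SAP 5.5.5.

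The effect is confined to a dedicated descriptive display and any grouping of thyroid terms. Event counts, listings, the primary comparison, power and the decision to proceed are untouched. The conclusion assumes that SAP 5.5.3 is applied literally, as SAP Table 1 directs. Whether the CRF carries the specific questions planned in Protocol 8.2 cannot be confirmed, because the eCRF is not among the documents.

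**What to change.** Add hypothyroidism to the list in SAP 5.5.3, state the MedDRA terms that make up the category, and include it in the separate tables of SAP 5.5.5. Replace the entry in SAP 6.0 with a line recording that the list of events of interest has been expanded beyond the protocol's three. If hypothyroidism was removed on purpose, declare and justify that in SAP 6.0 instead, and reconcile footnote c of SAP Tables 8-1 and 8-2 with Section 5.5.3.

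The cost is low: one term with its grouping, one table entry and one line of text. If the summary is meant to cover the lead-in phase, SAP 9.0 also needs a table title for events of interest. No new data collection should be needed if the CRF follows Protocol 8.2.

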**Table 4 Study Assessments for Physical Ability and Cognitive Function**

Test	Description	Possible Range of score	MCID/RCI from Baseline
Physical ability tests			
Timed Up and Go (TUG)	The TUG test is used to assess a person's mobility and requires both static and dynamic balance. It uses the time that a person takes to rise from a chair, walk three meters, turn around, walk back to the chair, and sit down.  Where possible, TUG time is to be measured by independent blinded assessors.	>1 second	1 second (Davies et al. 2016) [1]
Short Physical Performance Battery (SPPB)	The SPPB is a group of measures that combines the results of the gait speed, chair stand and balance tests.	0–12 points	0.5 points (Davies et al. 2016) [1]
Cognitive Tests			

Test	Description	Possible Range of score	MCID/RCI from Baseline
Hopkins Verbal Learning Test-Revised Total Recall (HVLTR TR)	The HVLTR is a learning and memory test, in which the participant is asked to learn and recall a list of 12 words over 3 trials.	0–36 words	±5 words (Wefel et al. 2011) [4]
Hopkins Verbal Learning Test-Revised Delayed Recall (HVLTR DR)	Spontaneous recall is assessed before and after a delay.	0–12 words	±3 words (Wefel et al. 2011) [4]
Hopkins Verbal Learning Test-Revised Delayed Recognition (HVLTR RECOG)	Recognition discriminability is also assessed after a delay. Four alternate versions of the test are used to minimize practice effects over time.	-12–+12 words	±2 words (Wefel et al. 2011) [4]
Trail Making Test (TMT) Part A (TMTA) Part B (TMTB)	
The TMTA assesses visual scanning and motor tracking requiring focused attention. Participants are required to sequentially connect numbered dots in ascending order that are randomly scattered across the test page.
 
TMTB includes a divided attention component requiring mental flexibility (i.e., executive function). On this subtest, dots with numbers and letters are randomly scattered on the test page. Participants are required to alternate between connecting numbers and letters in an ascending sequential order.
 
Both tests require the participants to complete the sequence as fast as possible. TMTA is discontinued after 3 minutes and TMTB is discontinued after 5 minutes for participants who have difficulty in order to reduce participant burden.
	1–2750 seconds 1–3750 seconds	±12 seconds ±26 seconds (Wefel et al. 2011) [4]
Controlled Oral Word Association (COWA)	The COWA test assesses lexical fluency. Given a specific letter of the alphabet, participants are required to produce as many words as possible that begin with that letter. There are two alternate forms of the COWA,	0 – unlimited words	±12 words (Wefel et al. 2011) [4]

Test	Description	Possible Range of score	MCID/RCI from Baseline
	each with three unique letter exemplars.		
Cognitive tests – Patient-reported outcomes			
Functional Assessment of Cancer Therapy-Cognitive (FACT-Cog)	The FACT-Cog questionnaire was developed to assess perceived cognitive function and impact on quality of life in cancer patients. It is a patient-reported outcome measure used to assess cognitive function in patients undergoing cancer therapy.	0–72 points	6.9-10.6 points (Cheung et al. 2014, Costa et al. 2018) [5]

Note: COWA = Controlled Oral Word Association; FACT-Cog = Functional Assessment of Cancer Therapy-Cognitive; HVLTR-DR = Hopkins Verbal Learning Test-Revised Delayed Recall; HVLTR-RECOG = Hopkins Verbal Learning Test-Revised Delayed Recognition; HVLTR-TR = Hopkins Verbal Learning Test-Revised Total Recall; MCID = minimal clinically important difference; RCI = reliable change index; SPPB = Short Physical Performance Battery; TMTA/TMTB = Trail Making Test Part A/B; TUG = Timed up and Go

